Total bilirubin $> 1.5 \times$ ULN*	
 
• Hold trabectedin and olaparib
 
• Monitor weekly total bilirubin until recovery to <math>\leq 1.5 \times</math> ULN, and then resume olaparib at current dose upon recovery.
 
• If peak bilirubin <math>\leq 3 \times</math> ULN, reduce trabectedin by one dose level at start of next cycle.
 
• At second recurrence, reduce trabectedin by next dose level
 
• If third recurrence or peak bilirubin <math>> 3 \times</math> ULN, permanently discontinue study treatment
 

AST or ALT* $> 2.5 \times$ ULN	
 
• Hold trabectedin and olaparib
 
• Monitor weekly LFTs until recovery <math>\leq 2.5 \times</math> ULN and then resume olaparib at current dose upon recovery.
 
• If peak value <math>> 2.5 \times</math> ULN and <math>\leq 5 \times</math> ULN, resume trabectedin at same dose at start of next cycle.
 
• If peak value <math>> 5 \times</math> ULN, reduce trabectedin by one dose level
 
• At second recurrence of peak value <math>> 5 \times</math> ULN, reduce trabectedin by one dose level.
 

ALP $> 2.5 \times$ ULN	
 
• Hold trabectedin
 
• Monitor weekly ALP until recovery to <math>\leq 2.5 \times</math> ULN
 
• Reduce trabectedin by one dose level
 
• At second occurrence, reduce trabectedin by one dose level
 

CK $> 2.5 \times$ ULN	
 
• Hold trabectedin
 
• Monitor weekly CK until recovery
 
• If peak value <math>> 2.5 \times</math> ULN-<math>5 \times</math> ULN, resume trabectedin at same dose.
 
• If peak value <math>> 5 \times</math> ULN, reduce trabectedin by one dose level
 
• At second occurrence of peak value <math>> 5 \times</math> ULN, reduce trabectedin by one dose level
 

\*In case a patient shows an AST or ALT  $\geq 3 \times \text{ULN}$  together with total bilirubin  $\geq 2 \times \text{ULN}$  please refer to Appendix A 'Actions required in cases of increases in liver biochemistry and evaluation of Hy's Law', for further instructions.

Table 5. Criteria for Dose modification of Non-Hematologic Adverse events

Adverse Event	Dose Adjustment

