**Appendix A      Actions Required in Cases of Increases in Liver Biochemistry and Evaluation of Hy's Law****Introduction**

This Appendix describes the process to be followed in order to identify and appropriately report cases of Hy's Law. It is not intended to be a comprehensive guide to the management of elevated liver biochemistries. Specific guidance on the managing liver abnormalities can be found in Section 5.2 of the protocol.

During the course of the study the Investigator will remain vigilant for increases in liver biochemistry. The investigator is responsible for determining whether a patient meets potential Hy's Law (PHL) criteria at any point during the study.

The Investigator participates, in review and assessment of cases meeting PHL criteria to agree whether Hy's Law (HL) criteria are met. HL criteria are met if there is no alternative explanation for the elevations in liver biochemistry other than Drug Induced Liver Injury (DILI) caused by the Investigational Medicinal Product (IMP).

The Investigator is responsible for recording data pertaining to PHL/HL cases and for reporting Adverse Events (AE) and Serious Adverse Events (SAE) according to the outcome of the review and assessment in line with standard safety reporting processes.

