### **Potential Hy's Law Criteria met**

If the patient does meet PHL criteria the Investigator will:

- Determine whether PHL criteria were met at any study visit prior to starting study treatment (See Actions Required When Potential Hy's Law Criteria are Met Before and After Starting Study Treatment)
- Notify the Company

The Coordinating Center/Study Principal Investigator contacts the Investigator, to provide guidance, discuss and agree an approach for the study patients' follow-up and the continuous review of data.

Subsequent to this contact the Investigator will:

- Monitor the patient until liver biochemistry parameters and appropriate clinical symptoms and signs return to normal or baseline levels, or as long as medically indicated
- Investigate the etiology of the event and perform diagnostic investigations as discussed with the Study Physician. << For studies using a central laboratory add: This includes deciding which the tests available in the Hy's law lab kit should be used>>
- Complete the three Liver CRF Modules as information becomes available
- If at any time (in consultation with the Study Physician) the PHL case meets serious criteria, report it as an SAE using standard reporting procedures

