## **Review and Assessment of Potential Hy's Law Cases**

The instructions in this Section should be followed for all cases where PHL criteria are met.

No later than 3 weeks after the biochemistry abnormality was initially detected, the Study Physician contacts the Investigator in order to review available data and agree on whether there is an alternative explanation for meeting PHL criteria other than DILI caused by the IMP. The AstraZeneca Medical Science Director and Global Safety Physician will also be involved in this review together with other subject matter experts as appropriate.

According to the outcome of the review and assessment, the Investigator will follow the instructions below.

If there is an agreed alternative explanation for the ALT or AST and TBL elevations, a determination of whether the alternative explanation is an AE will be made and subsequently whether the AE meets the criteria for a SAE:

- If the alternative explanation is **not** an AE, record the alternative explanation on the appropriate CRF
- If the alternative explanation is an AE/SAE, record the AE /SAE in the CRF accordingly and follow the AZ standard processes

---

If it is agreed that there is **no** explanation that would explain the ALT or AST and TBL elevations other than the IMP:

- Report an SAE (report term 'Hy's Law') according to AstraZeneca standard processes.
  - The 'Medically Important' serious criterion should be used if no other serious criteria apply
  - As there is no alternative explanation for the HL case, a causality assessment of 'related' should be assigned.

If, there is an unavoidable delay, of over 3 weeks, in obtaining the information necessary to assess whether or not the case meets the criteria for HL, then it is assumed that there is no alternative explanation until such time as an informed decision can be made:

- Report an SAE (report term 'Potential Hy's Law') applying serious criteria and causality assessment as per above
- Continue follow-up and review according to agreed plan. Once the necessary supplementary information is obtained, repeat the review and assessment to determine whether HL criteria are met. Update the SAE report according to the outcome of the review

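### For recovered potential Hy's Law cases with peak bilirubin of 2 to 3×ULN, no dosing rule makes restart wait for the Hy's Law review or requires a stop if Hy's Law is confirmed

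*Combined protocol and SAP*

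**What the plan says.** **Section 5.2, Table 4.** Bilirubin above 1.5×ULN, or AST/ALT above 2.5×ULN, holds both drugs. Both rows then call for weekly monitoring until recovery and "then resume olaparib at current dose upon recovery". If peak bilirubin is not above 3×ULN, trabectedin is reduced one level at the next cycle. The bilirubin row stops treatment permanently at a third recurrence or a peak above 3×ULN. For AST/ALT of at least 3×ULN with bilirubin of at least 2×ULN, the footnote adds "please refer to Appendix A 'Actions required in cases of increases in liver biochemistry and evaluation of Hy's Law', for further instructions".

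**Appendix A, Introduction.** The appendix states: "It is not intended to be a comprehensive guide to the management of elevated liver biochemistries". It continues: "Specific guidance on the managing liver abnormalities can be found in Section 5.2 of the protocol".

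**Appendix A, when potential Hy's Law criteria are met.** The Coordinating Center or Study Principal Investigator contacts the site "to provide guidance, discuss and agree an approach for the study patients' follow-up and the continuous review of data". The site monitors, investigates, completes the liver CRF modules and reports an SAE if serious criteria are met.

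**Appendix A, Review and Assessment.** The Study Physician's contact to review the case is due "No later than 3 weeks after the biochemistry abnormality was initially detected". If no explanation other than the investigational product is found, the site reports an SAE and "a causality assessment of 'related' should be assigned". If the needed information is unavoidably delayed beyond 3 weeks, "then it is assumed that there is no alternative explanation until such time as an informed decision can be made", and an SAE is reported on that basis.

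**The concern.** The footnote implies that potential Hy's Law needs something beyond the ordinary bilirubin and transaminase rows. The place it points to adds no dosing instruction and returns the reader to the section just left. What remains as a written dosing rule is the ordinary row, which directs resumption after recovery.

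Two things are therefore missing: a rule that restart waits for the review, and a rule that treatment stops if the review concludes Hy's Law. At stake is re-exposure to a drug that the protocol's own process has just judged to be the only explanation for the liver injury, or re-exposure while that question is open. This is a patient-safety matter in the dosing rules. It does not bear on the sample size or the response analysis.

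**Working it through.** The plan states no figure to reproduce. The check sets the rules side by side and then counts days.

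**1. Which patients are affected**
- Potential Hy's Law requires bilirubin of at least 2×ULN (Appendix A, Definitions).
- The Table 4 permanent stop requires a peak above 3×ULN, or a third recurrence.
- A peak of 2 to 3×ULN inclusive therefore meets the Hy's Law trigger without meeting the stop.
- Two other exits in Section 5.2 remove patients from this group: failure to meet the new-cycle criteria within 28 days of the initial hold, and exhausted dose reductions.

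**2. What each rule tests**

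| Rule | What it tests | Refers to the Hy's Law review? |
|---|---|---|
| Table 4, olaparib restart | Bilirubin ≤1.5×ULN, AST/ALT ≤2.5×ULN | No |
| New-cycle criteria (trabectedin) | Blood counts, bilirubin, AST/ALT, ALP, CK, related non-hematologic toxicity ≤ grade 2, no intolerable grade 2 event | No |
| Table 5, grade 3 or 4 toxicity | Ability to resume within 4 weeks; olaparib waits for the next cycle and both drugs are reduced at first occurrence | No |
| Appendix A, potential Hy's Law met | Notification, follow-up, work-up | Starts it; no dosing action |
| Appendix A, Hy's Law confirmed | SAE report, causality related | Is its outcome; no dosing action |

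**3. Comparison with other confirmed diagnoses**
- MDS/AML: discontinue when confirmed (Section 5.2).
- Pneumonitis: interrupt when suspected, discontinue when confirmed (Section 9.2).
- Hy's Law: no corresponding rule.

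**4. Timing, as an illustration only**

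Take day 0 as detection. Let R be the day recovery is documented, D the earliest day a dose is due, and V the day of the review. Days on drug before the review = max(0, V − max(R, D)). Fastest recovery under weekly checks gives R = 7. The latest scheduled review contact gives V = 21.
- Olaparib (D = 0): 21 − 7 = 14 days.
- Trabectedin, detected at the day 15 laboratory test (D = 22 − 15 = 7): 21 − 7 = 14 days.
- Trabectedin, detected at the day 8 test (D = 22 − 8 = 14; this test is required only in cycles 1 and 2): 21 − 14 = 7 days.
- If the review overruns, for example to V = 28, olaparib: 28 − 7 = 21 days.
- If recovery takes until day 21 and the review occurs by then: 0 days.

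Visit windows of ±3 days shift these values. The missing stop on confirmation does not depend on timing.

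**The case against.** The strongest reply is that the protocol does not leave such a patient unattended. Section 5.5 ends treatment for adverse events judged unacceptable, or when the investigator judges the patient's condition unfit for further treatment, and Section 5.6 makes removal follow. Section 5.8 allows withdrawal in the patient's best interest. The Coordinating Center or Study Principal Investigator contacts the site, AstraZeneca safety physicians join the review, SAEs are reported within 24 hours, and the DSMC reviews quarterly. All of this stands and makes an unconsidered rechallenge less likely. But each control depends on someone judging that a stop is needed while the dosing table says resume.

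A reader might infer several stronger things that the documents do not support:
- *Both drugs restart on laboratory values alone.* Trabectedin must also meet the new-cycle criteria, which include toxicity grade and tolerability, and it restarts at a reduced dose.
- *Every case in the 2 to 3×ULN band is restarted.* Patients who do not recover within 28 days, have a third recurrence or have exhausted their dose reductions come off treatment.
- *Fourteen days is the maximum exposure before review.* The 3-week limit applies to the contact to review, and Appendix A expressly provides for longer delay. Equally, many combinations of recovery and review dates give no early restart, and nothing in the documents says how likely any of them is.
- *Both drugs are implicated.* Appendix A attributes the injury to the investigational product without saying that both agents are responsible.

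It can also be said that the presumption of no alternative explanation after 3 weeks governs SAE reporting, not dosing. That is correct, and it argues against discontinuing automatically because a review is late. A lighter remedy, requiring Study Principal Investigator agreement before restart, would address the wait but would not supply a stop on confirmation.

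**Conclusion.** The concern holds for a defined group: potential Hy's Law with peak bilirubin of 2 to 3×ULN, not a third recurrence, dose reductions not exhausted, and recovery within 28 days. For these patients the written rules direct resumption, no restart criterion refers to the Hy's Law review, and confirmed Hy's Law triggers reporting but no dosing action. This is more than missing detail, because following the dosing table as written could re-expose a patient to an implicated drug. It should be fixed.

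The size cannot be stated as a frequency. The day counts assume recovery at the first weekly check and review at the 3-week contact limit. The conclusion is limited to the protocol text: the package insert, the Investigator Brochure and the AstraZeneca standard processes it refers to were not available.

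**What to change.** Add a Table 4 row for patients who meet the Appendix A definition of potential Hy's Law, including transaminase and bilirubin elevations on different days, since Appendix A sets no time limit between them. The row overrides the separate bilirubin and AST/ALT rows:

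1. Hold both drugs until the Appendix A review is complete.
2. Permanently discontinue study treatment if Hy's Law is confirmed.
3. If an alternative cause is agreed, resume under the existing rows, including their permanent-stop criteria.
4. If the review is still open after 3 weeks, keep holding. Any hold beyond 4 weeks is decided by the Study Principal Investigator, not by automatic discontinuation.

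Where Appendix A requires no new review (criteria already met before treatment, or certain repeat episodes, without significant change), the existing rows apply. Add a cross-reference from Appendix A to the new row.

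The cost is one table row and one sentence in an amendment, with no extra visits or tests. The cost to patients falls on cases that prove to have another cause: up to about 14 more days off treatment if reviewed by 3 weeks, and longer if the review overruns.

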#### **Guidance on renal impairment:**

If subsequent to study entry and while still on study therapy, a patient's estimated creatinine clearance (CrCl) falls below the threshold for study inclusion ( $\geq 51 \text{ ml/min}$ ), retesting should be performed promptly.

A dose reduction is recommended for patients who develop moderate renal impairment (calculated creatinine clearance by Cockcroft-Gault equation or based on a 24-hour urine test of between 31 and 50 ml/min) for any reason during the course of the study: the dose of olaparib should be reduced to 100 mg twice daily.

Because the CrCl determination is only an estimate of renal function, in instances where the CrCl falls to between 31 and 50 mL/min, the investigator should use his or her discretion in determining whether a dose change or discontinuation of therapy is warranted.

Olaparib has not been studied in patients with severe renal impairment (creatinine clearance  $\leq 30 \text{ ml/min}$ ) or end-stage renal disease; if patients develop severe impairment or end stage disease it is recommended that olaparib be discontinued.

#### **Management of new or worsening pulmonary symptoms**

If new or worsening pulmonary symptoms (e.g., dyspnea) or radiological abnormalities occur in the absence of a clear diagnosis, an interruption in study treatment dosing is recommended and further diagnostic workup (including a high resolution CT scan) should be performed to exclude pneumonitis.

Following investigation, if no evidence of abnormality is observed on CT imaging and symptoms resolve, then study treatment can be restarted, if deemed appropriate by the investigator. If

significant pulmonary abnormalities are identified, these need to be discussed with the Study Principal Investigator.

#### **Management of nausea and vomiting**

Events of nausea and vomiting are known to be associated with olaparib treatment. These events are generally mild to moderate (CTCAE grade 1 or 2) severity, intermittent and manageable on continued treatment. The first onset generally occurs in the first month of treatment for nausea and within the first 6 months of treatment for vomiting. For nausea, the incidence generally plateaus at around 9 months, and for vomiting at around 6 to 7 months.

No routine prophylactic anti-emetic treatment is required at the start of olaparib treatment, however, patients should receive appropriate anti-emetic treatment at the first onset of nausea or vomiting and as required thereafter, in accordance with local treatment practice guidelines. Alternatively, olaparib tablets can be taken with a light meal/snack (i.e. 2 pieces of toast or a couple of biscuits).

As per international guidance on anti-emetic use in cancer patients (ESMO, NCCN), generally a single agent antiemetic should be considered (e.g.) dopamine receptor antagonist, antihistamines or dexamethasone.

#### **Interruptions for intercurrent non-toxicity related events**

Study treatment dose interruption for conditions other than toxicity resolution should be kept as short as possible. If a patient cannot restart study treatment within 4 weeks for resolution of intercurrent conditions not related to disease progression or toxicity, the case should be discussed with the Principal Investigator.

All dose reductions and interruptions (including any missed doses), and the reasons for the reductions/interruptions are to be recorded in the patient's record.

Study treatment should be stopped at least 3 days prior to planned surgery. After surgery study treatment can be restarted when the wound has healed. No stoppage of study treatment is required for any needle biopsy procedure.

Study treatment should be discontinued for a minimum of 3 days before a patient undergoes radiation treatment. Study treatment should be restarted within 4 weeks as long as any bone marrow toxicity has recovered.

Because the AEs related to study treatment may include asthenia, fatigue and dizziness, patients should be advised to use caution while driving or using machinery if these symptoms occur.

#### **Special Considerations:**

- For ejection fraction reduction to < LLN or clinical evidence of cardiomyopathy, trabectedin should be held until normalization of EF. For absolute reduction in EF 10% or more from baseline and < LLN, reduce trabectedin to DL-1.

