#### 1.4.3 **Cardiotoxicity**

Whether trabectedin use in the treatment of sarcoma is associated with increased risk of cardiotoxicity is unclear. Earlier studies have suggested that the risk of drug-related cardiac adverse events was low, ranging from 0.2% to 7%. [27, 28] More recent studies have suggested that ventricular dysfunction occurs in up to 14% of patients with 3% in overt heart failure compared to 11% and 1% with dacarbazine.[29]

Soluble urokinase plasminogen activator receptor (suPAR) is a marker of immune activation and pathogenic factor in kidney disease. Levels of suPAR have been strongly associated with heart failure and incident cardiovascular disease.[30-32] We will measure suPAR along with traditional cardiovascular markers (BNP, high sensitivity troponin-I and high-sensitivity CRP) levels at baseline and after 2 doses of trabectedin, and determine whether levels are significantly altered by therapy, and whether baseline or early changes in levels are predictive of a later decline in left ventricular function.

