## 5.0 TREATMENT PLAN

### 5.1 Treatment Dosage and Administration

Protocol treatment must start within 14 business days of registration to the study.

Trabectedin 1.1 mg/m^2 will be administered intravenously over a 24-hour continuous infusion once every 21 days. Actual body weight from screening will be used to calculate dose. If weight changes by more than 10% from baseline, recalculate the dose.

Olaparib 150 mg tablets will be taken orally twice daily with a cycle length of 21 days. Olaparib should be taken at the same time every day, 12 hours apart with one glass of water. Olaparib can be taken with or without food. Tablets should be taken whole, not crushed or mixed into food. It is prohibited to consume grapefruit juice while on olaparib therapy. If vomiting occurs shortly after the olaparib tablets are swallowed, the dose should only be replaced if all of the intact tablets can be seen and counted. Should any patient enrolled on the study miss a scheduled dose for whatever reason (e.g., as a result of forgetting to take the tablets or vomiting), the patient will be allowed to take the scheduled dose up to a maximum of 2 hours after that scheduled dose time. If greater than 2 hours after the scheduled dose time, the missed dose is not to be taken and the patient should take their allotted dose at the next scheduled time.

Patients will be requested to maintain a medication diary of each dose of medication. The medication diary should be returned and/or reviewed by clinic staff at each scheduled clinic visit during the course of treatment.

REGIMENT DESCRIPTION					
Agent	Pre-medications; Precautions	Dose	Route	Schedule	Cycle Length
Trabectedin	Pre-medicate with dexamethasone 20 mg IV approximately 30 min prior to trabectedin. Pre-medicate with palonosetron 0.25 mg IV (or similar anti-emetic per institutional guidelines) prior to trabectedin	1.1 mg/m 	IV continuous infusion over 24 hours (+/- 2 hours)	Day 1	3 weeks (21 days)
Olaparib	It is prohibited to consume grapefruit, grapefruit juice and Seville oranges for duration of therapy. No routine prophylactic anti-emetic treatment is	150 mg	PO	BID, continuous	

	required; however, patients should receive appropriate anti-emetics in accordance with local treatment practice guidelines. Alternatively, olaparib tablets can be taken with a light meal/snack (i.e. 2 pieces of toast or biscuits).				
--	--	--	--	--	--

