## 5.2 Toxicities and Dosing Delays/Dose Modifications

Any patient who receives treatment on this protocol will be evaluable for toxicity. Each patient will be assessed for the development of toxicity according to the Time and Events Table (Section 6.2). Toxicity will be assessed according to the NCI Common Terminology Criteria for Adverse Events (CTCAE), version 5.0. Dose adjustments should be made according to the system showing the greatest degree of toxicity. Any toxicity observed during the course of the study could be managed by interruption of the dose of study treatment or dose reductions. Repeat dose interruptions are allowed as required, for a maximum of 4 weeks on each occasion. If the interruption is any longer, the study team must be informed. Once dose is reduced, escalation is not permitted

Table 1. Dose Level Reductions of Trabectedin and Olaparib

Dose Levels	Trabectedin	Olaparib
1 (starting)	1.1 mg/m 	150 mg BID
-1	0.94 mg/m 	100 mg BID
-2	0.8 mg/m 	

Criteria for start of new cycle:

- Platelet  $\geq$  100,000/microliter
- Absolute neutrophil count  $\geq$  1000/microliter
- Hemoglobin  $\geq$  9g/dl
- Total bilirubin  $\leq$  1.5 upper limit of normal (ULN)
- Aspartate aminotransferase (AST) and alanine aminotransferase (ALT)  $\leq$  2.5 x ULN
- Alkaline phosphatase (ALP)  $\leq$  2.5 x ULN
- Creatine phosphokinase (CK)  $\leq$  2.5 x ULN
- All non-hematologic toxicities considered related to study treatment must be  $\leq$  grade 2
- Absence of any subjectively intolerable grade 2 adverse event not controlled by supportive therapy

If a patient does not meet criteria to initiate a new cycle of treatment within 28 days of initial medication hold, or requires more than two dose reductions of trabectedin or one dose reduction of olaparib, they should be removed from study treatment.

For hematologic toxicities which meet parameters for dose hold, medication should be held per guidance below. Medication should be resumed at the reduced dose designated below. If AE is recurrent/persistent despite dose reduction as specified below, drug should be discontinued.

Table 2. Criteria for Dose modification of Thrombocytopenia, Neutropenia and Leukopenia

Laboratory Result	Dose Adjustments

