- i. Transthoracic echocardiogram (TTE) will be obtained at baseline to ensure adequate LVEF. Repeat TTE will be obtained every 3 cycles ( $\pm 1$  cycles) while on trabectedin or if clinical concern of decline in ejection fraction. MUGA can be performed if inadequate assessment by TTE per standard practice.
- j. Assessment of cardiovascular biomarkers including suPAR, BNP, high-sensitive troponin-I and high-sensitivity CRP will be obtained at baseline and after 2 doses of trabectedin on cycle 3 day 1.
- k. Results of NGS (if available) and archival tumor tissue to test for the presence of alterations in DNA repair pathways. Patients will not be asked to undergo an additional biopsy to obtain tumor sample. Full reports must be provided by the investigator for documentation on the Patient Safety database. These data are not required to be entered into CRF.
- l. Bone marrow or blood cytogenetic samples may be collected for patients with prolonged hematological toxicities at any timepoint as clinically indicated as defined in Section 5.2. Bone marrow analysis should include an aspirate for cellular morphology, cytogenetic analysis and flow cytometry, and a core biopsy for bone marrow cellularity. If it is not possible to conduct cytogenetic analysis or flow cytometry on the bone marrow aspirate, then attempts should be made to carry out the tests on a blood sample.
- m. Patients will be followed every 3 months via phone for documentation of progression and survival status for a minimum of 2 years from registration. If patient is unavailable, then survival status will be determined if possible, by public available information.
- n. Visits on day 1 of each cycle, lab measurements at days 1, 8 and 15 of each cycle, and the end of treatment visit, can be completed  $\pm 3$  days.

\* Screening labs to be obtained within 14 days of initiation of therapy. Baseline imaging to be obtained within 28 days of initiation of therapy.

\*\* Laboratory assessment will be done on day 8 for first 2 cycles to monitor for cytopenias.

Continued day 8 laboratory assessment beyond cycle 2 is at the discretion of the treating physician.

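### The ejection-fraction rule in section 5.2 sends trabectedin to a fixed level, so read against Table 1 it reduces the dose only from the starting level, and the protocol does not say which time limit governs the accompanying hold

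*Combined protocol and SAP*

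**What the plan says.** Section 5.2, Special Considerations, gives two instructions for a fall in EF. When EF drops below the lower limit of normal (LLN), or there is clinical cardiomyopathy, "trabectedin should be held until normalization of EF". For a larger fall, the dose step is: "For absolute reduction in EF 10% or more from baseline and < LLN, reduce trabectedin to DL-1".

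The rest of section 5.2 supplies the context:

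- Table 1 lists trabectedin at level 1 (1.1 mg/m2), -1 (0.94) and -2 (0.8).
- The opening text states: "Once dose is reduced, escalation is not permitted".
- The other trabectedin reductions, in Tables 2, 4 and 5, are relative. The bilirubin row of Table 4, for example, reads "reduce trabectedin by one dose level at start of next cycle".
- The text below the new-cycle criteria begins "If a patient does not meet criteria to initiate a new cycle of treatment within 28 days of initial medication hold" and ends in removal from study treatment. The same sentence removes patients who need more than two trabectedin reductions.
- The opening text also limits each interruption to 4 weeks, but asks only that the study team be told if it runs longer.
- Table 5 withdraws patients with certain non-hematologic toxicities who cannot resume within 4 weeks.

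Section 6.2, footnote i, sets the monitoring: "Repeat TTE will be obtained every 3 cycles", give or take one cycle, while on trabectedin, with a further echocardiogram if a decline is suspected clinically.

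**The concern.** A dose-modification rule has to give a defined action from every dose a patient can be on. A rule that names a destination rather than a step does so only if all patients start above that destination. Here there are two reduced trabectedin levels, and patients can reach either for blood counts, liver tests, creatine phosphokinase or other toxicity before any cardiac event.

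The hold raises a second question. It ends when EF normalizes, but the document does not say how long that may take before the patient leaves treatment, or when EF must be re-measured.

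The stake is first a safety one: two sites could handle the same cardiac finding differently. There is a smaller analytical stake. Objective 2.3.3 and section 10.3 ask whether biomarkers predict LVEF decline. Whether a patient is re-dosed, removed or kept on hold affects later exposure, later LVEF readings and the discontinuation count.

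**Working it through.** **Dose step.** The inputs are the three trabectedin rows of Table 1. Change = target / current - 1.

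| Current level | Current dose (mg/m2) | If DL-1 is the row labelled -1 | If DL-1 means one level down |
|---|---|---|---|
| 1 | 1.1 | 0.94; 0.94/1.1 - 1 = -14.5% | 0.94; -14.5% |
| -1 | 0.94 | 0.94; 0.94/0.94 - 1 = 0% | 0.8; 0.8/0.94 - 1 = -14.9% |
| -2 | 0.8 | 0.94; 0.94/0.8 - 1 = +17.5%, barred elsewhere in 5.2 | no row exists; would be a third reduction |

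The two readings agree only at level 1. The gap at level -1 does not need earlier non-cardiac toxicity. A patient reduced from 1.1 to 0.94 for a first EF event, then held and reduced again under the rule for a second, stays at 0.94 on the fixed reading. The trabectedin rules in Tables 2, 4 and 5 say what to do at a recurrence; the EF rule does not.

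Section 5.2 also names a fixed target for olaparib (100 mg twice daily, for anemia and renal impairment). That causes no such difficulty, because Table 1 gives olaparib only one reduced level.

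**Hold.** Three provisions could govern an EF hold that reaches four weeks:

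1. Removal from study treatment at 28 days. This depends on the new-cycle criteria, which do not name EF. The nearest item is the general one on treatment-related non-hematologic toxicity of grade 2 or less, so an EF fall judged unrelated, or graded 2 or lower, would not fail that item.
2. Continuation, with the study team informed.
3. Withdrawal under Table 5, if the event falls within its categories.

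The EF bullet refers to none of them.

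**Echocardiogram timing.** Cycles last 21 days.

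- Nominal interval: 3 x 21 = 63 days.
- Window counted from the last echo: (3 - 1) x 21 = 42 to (3 + 1) x 21 = 84 days.
- Window anchored to the nominal schedule, with a late echo followed by an early one: (3 - 1 - 1) x 21 = 21 days.

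A scheduled repeat may therefore fall before or after day 28. If the abnormal echo was itself unscheduled, the next scheduled one may come sooner still. The scheduled series is tied to being on trabectedin, and the extra echo is triggered by suspected decline. Nothing requires one to document recovery during a hold.

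**Size.** Section 1.4.3 says "ventricular dysfunction occurs in up to 14% of patients". Maximum enrolment is 26 + 27 = 53.

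- Upper figure for the hold rule: 0.14 x 53 = 7.4, about 7 patients, assuming the rate applies to both cohorts.
- The same section gives 0.2% to 7% for drug-related cardiac adverse events in earlier studies. This is a different outcome, but as a lower guide: 0.002 x 53 = 0.1 to 0.07 x 53 = 3.7.
- The documents do not give the share already dose-reduced when EF falls. If it were 10% to 30% (an assumption), the dose-step gap would reach at most 0.10 x 7.4 = 0.7 to 0.30 x 7.4 = 2.2 patients, not counting second EF events. It would be fewer still because the dose step also needs a fall of 10% or more from baseline.

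**The case against.** The strongest reply is that the rest of section 5.2 limits the harm, and much of that stands.

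- **Escalation.** A reader might infer that a patient at 0.8 mg/m2 is ordered up to 0.94. The documents do not support that. The EF rule says to reduce, escalation is forbidden, and a third trabectedin reduction leads to removal. What remains at level -2 is an instruction that conflicts with its neighbours.
- **Meaning of DL-1.** DL is not in the abbreviation list, and Table 1 does not use it. One level down is a possible reading and would match the other rules. That moves the problem without removing it, because the text supports both readings and they differ at level -1.
- **No response to later EF events.** This would be wrong. The hold applies at every dose level and every occurrence; only the dose step is unclear.
- **An irreconcilable hold.** A hold until recovery can coexist with a general time limit, and the bilirubin and transaminase rows of Table 4 are built that way. The surviving point is narrower: section 5.2 gives different consequences at about four weeks and does not say which covers an EF hold.
- **Recovery cannot be shown within 28 days.** This does not follow. The schedule can yield a reading inside 28 days in some cases, and ending the hold implies a repeat reading. The gap is that its timing is unstated.

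**Conclusion.** The point holds as an internal inconsistency in a safety rule. On the fixed-level reading, the EF dose step is a reduction only from level 1, has no effect at level -1, and is undefined at level -2. On the alternative reading it works at level -1, but the text does not say that this is meant. At level -1 no other sentence corrects the fixed reading, since staying at 0.94 mg/m2 breaks no rule. Separately, the time limit on an EF hold, its relation to the new-cycle criteria and the timing of the deciding echocardiogram are not stated.

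The numbers are small: at most about 7 of 53 patients for the hold, if the cited upper rate applies to both cohorts at full enrolment, and an unknown smaller number for the dose step. Cardiotoxicity is an exploratory objective that section 11.3 treats descriptively, and the error rates of the two Simon designs do not depend on this rule. It should be corrected because it governs a cardiac safety signal and costs little to clarify.

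**What to change.** The sponsor should reconcile section 5.2 (opening text, Table 1, new-cycle criteria, Table 5 and Special Considerations) with section 6.2 footnote i, and state:

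1. what DL-1 means for a patient currently at level 1, -1 or -2, and at a second EF event, consistently with the escalation ban and the removal rule;
2. which of the time provisions applies to an EF hold;
3. how the hold relates to the new-cycle criteria, which do not name EF;
4. when the echocardiogram that decides the hold is obtained.

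The dose and the clinical rule are for the sponsor to choose; the request is only that the sections agree. The cost is a few sentences in section 5.2 and a clause in footnote i. The downside is an occasional earlier repeat echocardiogram in the few patients on an EF hold, who need a repeat reading to end the hold in any case.
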